6 STUDY INTERVENTION

This study is a comparison of two treatment strategies for refractory out-of-hospital cardiac arrest (OHCA): continued standard care in the field (control) versus expedited transport with ongoing mechanical CPR to a hospital capable of initiating extracorporeal cardiopulmonary resuscitation (ECPR) in the emergency department (experimental). ECPR is defined as percutaneous veno-arterial extracorporeal membrane oxygenation (ECMO) initiated during cardiac arrest. The duration of ECPR is typically 72 hours to allow the patient's heart function to recover prior to weaning. Many devices make up an ECMO circuit (cannulas, conduit, reservoir, pump, oxygenator, heat exchanger, monitors, sweep gas controller, bubble traps, blood filters, positive and negative pressure monitors and controls). The devices used for ECMO are FDA-approved for up to 6 hours for the indication of cardiopulmonary bypass. However, ECPR for the treatment of refractory cardiac arrest is not a FDA approved or cleared indication for ECMO devices, and thus is considered investigational in this study. Current American Heart Association Guidelines state that *"In settings where it can be rapidly implemented, ECPR may be considered for select cardiac arrest patients for whom the suspected etiology of the cardiac arrest is potentially reversible during a limited period of mechanical cardiorespiratory support (Class IIb, LOE C-LD)"*. ECPR is currently performed in the University of Michigan University Hospital ED for selected patients with refractory cardiac arrest as part of our standard practice. Examples of local guidelines for EMS and ED care are given as appendices B and C.

7 STUDY PROCEDURES AND SCHEDULE

7.1 STUDY PROCEDURES/EVALUATIONS

7.1.1 Study specific procedures

Consent Process

Participants or their legally authorized representative (LAR) or family member will be approached within a reasonable timeframe and will be requested for consent to continue in the study. The availability and emotional state of LAR/family members will be taken into account, and anticipate a longer timeframe in these situations. The progress of obtaining written informed consent will be documented in the medical record. For participants who do not survive to hospital admission, a letter will be sent as notification.

Review of Medical Records

FDA's regulations require clinical investigators to prepare and maintain adequate and accurate case histories (21 CFR 312.62(b) and 812.140(a)). In general, the investigator should arrange to have access to all records that are generated and maintained from enrollment until discharge or death, unless the participant or their LAR/family member discontinues the participant's participation in the study. Medical records will be reviewed by a member of the research team up until this time and if the participant or LAR or family member discontinues participation, the data already collected will remain with the study.

Prehospital Medical Records

BLS and ACLS run reports will be reviewed on all study participants by the study team and study specific data abstracted. Run reports become part of the medical record when patients are brought to the emergency department and for cardiac arrests pronounced dead in the field, will be sent to the study team securely (i.e. by fax).

The following scales will be performed by a member of the research team at hospital discharge and Day 90, in participants who survive.

Modified Rankin Scale (mRS)

The mRS is commonly used for measuring the degree of disability or dependence in the daily activities of people who have suffered a neurological disability. mRS score is widely used in stroke research.

Cerebral Performance Categories Scale (CPC)

CPC score is widely used in cardiac arrest research to assess neurologic outcome.

NIH Toolbox

The NIH toolbox includes several cognitive, motor, and psychological tests. It can be administered via an iPad.

7.1.2 STANDARD CARE STUDY PROCEDURES

Standard care for the treatment of OHCA will include cardiac defibrillators, mechanical CPR, intravenous (IV) therapy, arterial blood pressure monitoring, central line monitoring, intubation, mechanical ventilation, heart monitoring, cardiac catheterization, hypothermic

targeted temperature management, and continuous EEG monitoring. Standard procedures for engaged prehospital providers/agencies and qualified emergency departments will be followed. Examples of prehospital and in-hospital standard care protocols are given as appendices B and C.

7.2 LABORATORY PROCEDURES/EVALUATIONS

7.2.1 CLINICAL LABORATORY EVALUATIONS

No biological materials, including blood samples, will be obtained as part of this study protocol.

7.3 STUDY SCHEDULE

7.3.1 SCREENING

Screening (Day 0, Field Baseline)

Screening will be done by prehospital providers in all out-of-hospital cardiac arrests in the engaged agencies area. All out-of-hospital cardiac arrests, meeting inclusion criteria will be considered for the study.

Pre Enrollment – Treatment Group Assignment / Randomization

At the time of dispatch of EMS, the dispatcher will enter the address of the arrest, age of the patient, and time of 911 call into a web form. The form will use an application to determine whether the patient is within the travel distance to arrive at the hospital within the pre-specified interval. They will immediately receive one of the following messages:

- 1) Not eligible, continue usual resuscitative care (patient may be out of geographic time area, may be over 71 years old)
- 2) Eligible, randomized to usual care
- 3) Eligible, randomized to early transport.

If the dispatcher is unable to access the assignment/randomization website, there will be a study team member, with access rights to the website available by telephone at all times.

7.3.2 ENROLLMENT/BASELINE

Pre-hospital run sheet(s) will be reviewed for study eligibility and enrollment criteria. The emergency department and hospital electronic medical record will be reviewed for continued inclusion criteria, including time intervals from 911 call to randomization and 911 call to

emergency department admission, if applicable. Until hospital discharge, all data collected will come from previously collected medical records.

Initial Enrollment/Field Baseline (Day 0)

Patients will be enrolled and randomized if they meet the inclusion criteria, namely, the presence of refractory cardiac arrest (defined as no ROSC after initial rhythm analysis and shock if indicated). The treatment group was pre-assigned during the screening phase, but patients with immediate ROSC are considered screened out of the study as no experimental intervention will occur to them.

Patients with persistent cardiac arrest in the field who are randomized will be followed for clinical outcomes per the protocol whether or not they have ECPR.

Due to the sudden and urgent nature of cardiac arrest, treatment must occur immediately. Enrollment will occur at the time of randomization by the prehospital providers at the scene of the out-of-hospital cardiac arrest. Patients will be enrolled under the exception from informed consent (EFIC) process.

Prehospital Medical Records

Prehospital run reports is where Basic Life Support (BLS) and Advanced Life Support (ALS) document the events of the 911 call and often become part of the medical record when patients are brought to the emergency department. Any run reports not found in the medical record and for participants who dies prior to the emergency department will be collected directly from the agencies.

EMS medical records will be reviewed and the following data abstracted:

- Date and time of 911 call
- Time of index cardiac arrest
- Status of witnessed arrest
- Status of Bystander CPR
- Time of collapse
- Time CPR initiated
- Duration of EMS CPR
- Initial recorded cardiac arrest rhythm
- Use of Impedance-threshold device
- Use and type of advanced airway
- Location of cardiac arrest (home, public place, parking lot, street, etc.)
- Date and time of ED arrival

Index Cardiac Arrest/Emergency Department (Day 0)

Emergency Department (ED) medical records will be reviewed and the following data abstracted:

- Date and time of ED arrival
- Status and timing of ROSC
- Demographic information
- Physician progress note(s)
- Past medical history; known comorbidities
- Nurses notes
- Tests performed and their results
- Procedures performed and their outcome
- Status of ECPR procedure
 - Time of confirmed placement of arterial and venous ECMO catheters
 - Time of initiation of ECPR
- ED Discharge diagnosis
- ED disposition

Survival to Hospital Admission (Day 0- Hospital Discharge or Death)

Attempt to notify the participant, LAR, or family member of study participation and seek permission to continue in the study, using the written IRB approved informed consent form.

Hospital medical records will be reviewed and the following data abstracted:

- Date and time of Hospital admission
- Status of ROSC
- Use of therapeutic hypothermia
- Neurologic status
- Physician progress note(s)
- Nurses notes
- Tests performed and their results
- Procedures performed and their outcome
- Assess for serious adverse events

Hospital Discharge

Hospital medical records will be reviewed and the following data abstracted:

- Date and time of Hospital discharge
- Survival status
- Assess for serious adverse events
- Discharge disposition

The following assessments will be performed by a member of the study team:

- CPC
- mRS
- NIH Toolbox Cognitive Testing

Assess for Serious Adverse Events (SAE's)

Prehospital and hospital records will be reviewed for serious adverse events.

7.3.3 FOLLOW-UP

Follow-up Visit (Day 90 +/- 15 days)

The following assessments will be performed by a member of the study team:

- CPC
- mRS
- NIH Toolbox Cognitive Testing
- Quality of Life Survey

7.3.4 FINAL STUDY VISIT

Final study visit is the Day 90 visit described above in section 7.3.3. The study participant will be contacted by telephone to set up a follow up appointment. Reasonable costs such as parking, bus fare, or mileage will be covered by the study.

7.3.5 EARLY TERMINATION VISIT

Prehospital patients in cardiac arrest will not have the ability to notify prehospital providers of their choice to participate or not. If a LAR/family member is aware of the study and objects to their participation, prehospital providers will not enroll the patient.

If the participant survives to hospital admission, a member of the study team will attempt to contact the participant or LAR/family member to notify them of study participation and obtain informed consent for continued participation in the study. The participant or LAR or family member has the right to decline study participation at any time before or after informed consent is obtained. A participant, however may not withdraw use of the data already collected. At the point of termination, the medical record will no longer be reviewed. However, data about a participant's death is contained in public vital statistics records. Access to public records is not subject to restriction under 21 CFR 50.24 or other FDA regulations.

7.3.7 SCHEDULE OF EVENTS TABLE

Procedures	Index Cardiac Arrest (Field)	Emergency Department	Survival to Hospital Admission	Hospital Course	Hospital Discharge	End of Study/Day 90
Screening	X					
Enrollment	X					
Randomization	X					
ROSC	X	X				
Survival Status	X	X	X	X	X	X
Review of pre-hospital medical	X					
Review of medical record	X	X	X	X	X	X
Informed Consent Process		X				X
CPC					X	X
mRS					X	X
NIH Toolbox					X	X
Quality of Life Survey						X
Monitor Serious Adverse Events	X	X	X	X	X	X

ROSC – Return of Spontaneous Circulation

CPC – Cerebral Performance Category

mRS – Modified Rankin Scale

7.4 JUSTIFICATION FOR SENSITIVE PROCEDURES

Not applicable.

7.5 CONCOMITANT MEDICATIONS, TREATMENTS, AND PROCEDURES

Clinical care is at the discretion of the clinical team. No concomitant medications, treatments or procedures are required or prohibited by the research protocol.

8 ASSESSMENT OF SAFETY

8.1 SPECIFICATION OF SAFETY PARAMETERS

Predefined safety clinical events are outlined in the endpoints sections 4.2.2 and 4.2.3. Since the study intervention is early transport versus continued resuscitation in the field, and all interventions occurring after this intervention represent standard care, safety endpoints will provide a qualitative assessment of the strategies given the limited sample size. Summaries of

events by group will be provided to all relevant monitoring bodies. Given the severity of cardiac arrest, most patients will experience one or more SAEs as part of routine clinical care.

8.1.1 DEFINITION OF ADVERSE EVENTS (AE)

An adverse event (AE) is any unfavorable and unintended sign (including a clinically significant abnormal laboratory finding), symptom, or disease temporally associated with the use of a medical treatment or procedure regardless of whether it is considered related to the medical treatment or procedure (attribution of unrelated, unlikely, possible, probable, or definite). Each AE is a unique representation of a specific event used for medical documentation and scientific analysis.

8.1.2 DEFINITION OF SERIOUS ADVERSE EVENTS (SAE)

A serious adverse event (SAE) is an AE that is fatal or life threatening, is permanently or substantially disabling, requires or prolongs hospitalization, results in a congenital anomaly, requires intervention to prevent permanent impairment or damage, or any event that the treating clinician or internal medical monitor judges to be a significant hazard, contraindication, side effect, or precaution. Reporting serious adverse events (SAEs) are based on the guidelines of the International Conference on Harmonization (ICH).

8.1.3 DEFINITION OF UNANTICIPATED PROBLEMS (UP)

OHRP considers unanticipated problems involving risks to participants or others to include, in general, any incident, experience, or outcome that meets all of the following criteria:

- Unexpected in terms of nature, severity, or frequency given (a) the research procedures that are described in the protocol-related documents, such as the IRB-approved research protocol and informed consent document; and (b) the characteristics of the participant population being studied;
- Related or possibly related to participation in the research (“possibly related” means there is a reasonable possibility that the incident, experience, or outcome may have been caused by the procedures involved in the research); and
- Suggests that the research places participants or others at a greater risk of harm (including physical, psychological, economic, or social harm) than was previously known or recognized.

This study will use the OHRP definition of UP.

This definition could include an unanticipated adverse device effect, any serious adverse effect on health or safety or any life-threatening problem or death caused by, or associated with, a device, if that effect, problem, or death was not previously identified in nature, severity, or degree of incidence in the investigational plan or application, or any other

unanticipated serious problem associated with a device that relates to the rights, safety, or welfare of subjects (21 CFR 812.3(s)).

8.2 CLASSIFICATION OF AN ADVERSE EVENT

8.2.1 SEVERITY OF EVENT

‘Severity’ is not the same as ‘serious.’ Serious is based on patient/event outcome or action criteria usually associated with events that pose a threat to a patient’s life or health. The term ‘severe’ is often used to describe the intensity (severity) of a specific event (as in mild, moderate, severe myocardial infarction); the event itself, however, may be of relatively minor medical significance (such as severe headache). Seriousness (not severity) serves as a guide for defining regulatory reporting obligations. Most AEs include clinical criteria that describe patient/event outcomes or indicated interventions to more clearly substantiate seriousness.

All adverse events occurring within 24 hours of study enrollment and all serious adverse events occurring during study participation will be documented on the AE case report form. Adverse events will be documented using the NCI Common Terminology Criteria for Adverse Events Version 3.0 (CTCAE). The CTCAE provides descriptive terminology that will be used for recording and reporting adverse events that occur in the EROCA trial. The CTCAE provides a grading (severity) scale for each AE term and AEs are listed alphabetically within categories based on anatomy or pathophysiology. The CTCAE (v 3.0) displays Grades 1-5 with unique clinical descriptions of severity for each AE based on this general guidance:

Grade 1:	Mild AE
Grade 2:	Moderate AE
Grade 3:	Severe AE
Grade 4:	Life-Threatening or Disabling AE
Grade 5:	Death related to AE

Note: Severity is not equivalent to seriousness. A serious adverse event (SAE) would be any event in category 4 or 5, and any event in category 3 that required or prolonged hospitalization.

Not all grades are appropriate for all AEs. Therefore, some AEs are listed with fewer than five options for Grade Selection i.e., Grade 5 (Death) is not appropriate for some AEs and therefore is not an option. A version of the CTCAE is available in the MoP

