8.3 TIME PERIOD AND FREQUENCY FOR EVENT ASSESSMENT AND FOLLOW-UP

The occurrence of an AE or SAE may come to the attention of study personnel during study visits and interviews of a study participant presenting for medical care, or upon review by a study monitor. All AEs including local and systemic reactions not meeting the criteria for SAEs will be captured on the appropriate RF. Information to be collected includes event description, time of onset, clinician's assessment of severity, relationship to study product (assessed only by those with the training and authority to make a diagnosis), and time of resolution/stabilization of the event. All AEs occurring while on study must be documented appropriately regardless of relationship. All AEs will be followed to adequate resolution.

Any medical condition that is present at the time that the participant is screened will be considered as baseline and not reported as an AE. However, if the study participant's condition deteriorates at any time during the study, it will be recorded as an AE. UPs will be recorded in the data collection system throughout the study.

Changes in the severity of an AE will be documented to allow an assessment of the duration of the event at each level of severity to be performed. AEs characterized as intermittent require documentation of onset and duration of each episode.

The PI or designated research staff will record all reportable events with start dates occurring any time after study enrollment until 24 hours (for non-serious AEs) or 90 days or last day of study participation (for SAE's). At each study visit, the investigator or study coordinator will inquire about the occurrence of SAEs since the last visit. Events will be followed for outcome information until resolution or stabilization.

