8.4.1 ADVERSE EVENT REPORTING

All AEs occurring within 24 hours of study participation and all serious adverse events (SAEs) occurring up until 90 days or last day of study participation are recorded on the online AE case report form (CRF) through the study database. The Site PI or Study Coordinator or designee is responsible for entering any and all AEs and SAEs into the database as soon as he/she becomes aware of the event and updating the information (e.g., date of resolution, action taken) in a timely manner. All non-serious AEs must be recorded on the electronic AE CRF within 5 days from the time it was discovered by the site study personnel. (All non-serious AEs during hospitalization must be entered within 5 days of discharge or end of study for that subject.) For SAEs, the data entry must take place within 24 hours of discovery of the event.

The Site PI is responsible for the monitoring and follow-up of AEs until resolution (or end of study for that subject) and appropriate documentation in the subject research record. In addition to performing protocol-specified follow up, the participating PI must review all previously reported ongoing AEs to evaluate the current status. If an AE that was previously reported on the Adverse Event CRF fully resolves and then recurs at a later date, the second occurrence is considered a new AE and a new Adverse Event CRF must be completed. Likewise, if an SAE that was previously reported and subsequently fully resolved later recurs at a level requiring expedited reporting, the SAE must be reported as a new SAE on the Adverse Event CRF.

Upon completion of the study protocol by the subject, premature withdrawal from the study by the subject, or subject's death, all information regarding each AE must be completed, if not done so earlier.

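### Section 8.2.1 gives a grade-based rule for a serious adverse event that is narrower than the definition in 8.1.2 and 8.4, so the same event after 24 hours can be on the SAE record under one rule and off it under the other

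*Combined protocol and SAP*

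**What the plan says.** Section 8.1.2 defines an SAE by what the event did or what had to be done about it. Besides fatal and life-threatening events, it includes an event that "is permanently or substantially disabling, requires or prolongs hospitalization, results in a congenital anomaly", and it continues: "requires intervention to prevent permanent impairment or damage, or any event that the treating clinician or internal medical monitor judges to be a significant hazard". Contraindications, side effects and precautions judged significant are covered in the same clause. No CTCAE grade is mentioned. Section 8.4 (Reporting Procedures) repeats this definition.

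Section 8.2.1 begins from the same principle: "Seriousness (not severity) serves as a guide for defining regulatory reporting obligations". A note below the CTCAE grading table repeats that severity and seriousness differ, and then says: "A serious adverse event (SAE) would be any event in category 4 or 5, and any event in category 3 that required or prolonged hospitalization".

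Three places make recording depend on the label:

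- 8.2.1: "All adverse events occurring within 24 hours of study enrollment and all serious adverse events occurring during study participation will be documented" on the AE form.
- 8.3: start dates are covered "until 24 hours (for non-serious AEs) or 90 days or last day of study participation", the second limit being for SAEs.
- 8.4.1: "All AEs occurring within 24 hours of study participation and all serious adverse events (SAEs) occurring up until 90 days", or the last day of participation, are recorded on the online form.

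Section 8.6 gives the DSMB all SAEs by group and a listing of SAEs for each patient. Section 10.4.4 makes the final safety analysis an SAE summary by group with a listing.

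**The concern.** Seriousness is meant to be separate from severity, yet the 8.2.1 note determines it from grade. The note has no route for an event that "requires intervention to prevent permanent impairment or damage", none for clinical judgement, and none for a grade 1 or 2 event that requires or prolongs hospitalization. A coordinator who grades an event and then applies the note can reach a different answer from one who applies 8.1.2 to the same chart.

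The hospitalization test in the note also separates events poorly here. A patient with a late complication may already be in hospital for a long stay, so an event that needs active treatment need not lengthen it.

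At stake is the completeness and reproducibility of the SAE record. Estimating the frequency of adverse events is a stated objective (Section 3). The trial has at most 30 patients and no quantitative stopping rule (8.5), so the DSMB relies on reading tables and listings, where a few events classified differently would be visible.

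**Working it through.** The protocol gives no figure to reproduce on this point. The check sets the two rules side by side and counts where they part.

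**Inputs.** Rule A is the outcome/action definition in 8.1.2 and 8.4. Rule B is the grade-based note in 8.2.1. The grade descriptions come from the 8.2.1 table.

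**Step 1: grades 4 and 5.** Grade 4 is described as life-threatening or disabling and grade 5 as death related to the event. Both are serious under Rule B by grade and under Rule A by outcome. There is no disagreement here.

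**Step 2: grades 1 to 3.** Cross grade (1, 2, 3) with hospitalization required or prolonged (yes/no) and intervention needed to prevent permanent damage (yes/no). That gives 3 × 2 × 2 = 12 combinations. The other Rule A criteria, including clinical judgement, are set aside.

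| Hospitalization | Intervention | Rule A, any grade | Rule B, grade 3 | Rule B, grades 1 and 2 |
|---|---|---|---|---|
| yes | yes | serious | serious | not serious |
| yes | no | serious | serious | not serious |
| no | yes | serious | not serious | not serious |
| no | no | not serious | not serious | not serious |

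- Serious under Rule A: 3 of 4 rows × 3 grades = 9.
- Serious under Rule B: 2, both at grade 3 with hospitalization.
- Every Rule B event is also a Rule A event, so the rules disagree in 9 − 2 = 7 of 12.
- Among the 6 combinations that needed intervention, Rule A calls all 6 serious and Rule B only 1, so they disagree in 5.
- Clinical judgement, set aside above, adds further disagreement in the same direction.

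These counts show how far the definitions differ. They are not expected numbers of events, because the documents give no frequencies by grade, hospitalization or intervention.

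**Step 3: follow one disagreeing event.** Take a grade 3 complication with onset after 24 hours in an inpatient. It needs intervention to prevent permanent damage but does not lengthen the stay.

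- Under 8.1.2 and 8.4 it is an SAE: inside the 90-day window, due in the database within 24 hours of discovery (8.4.1, 8.4.2), in the DSMB listing (8.6) and in the 10.4.4 summary.
- Under the 8.2.1 note it is non-serious. Its onset is past the 24-hour limit in 8.2.1, 8.3 and 8.4.1, so it is outside the AE window and absent from the SAE tables.

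**Step 4: look for a tie-breaker.** None of 8.1.2, 8.2.1, 8.3, 8.4, 8.6 or 10.4.4 says which rule prevails.

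**The case against.** The best defence is that the sentence is only a note under a severity heading. It follows a reminder that severity is not seriousness, and it does not use the word only. It could be read as listing grades that are enough for seriousness, with 8.1.2 and 8.4 supplying the full definition. Someone working from 8.4 would apply the full wording. That reading is possible, but the note is worded as a definition and nothing subordinates it to 8.1.2. The defence supports one of the two fixes below; it does not remove the conflict.

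Four stronger readings are tempting, and the documents do not support them.

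- *A complication after 24 hours goes unrecorded altogether.* Vessel damage needing a procedure is a component in 4.2.2, and limb ischemia is in the synopsis composite. Section 10.3 collects safety endpoints on all enrolled patients, 4.2.3 reports the 4.2.2 components individually, and 7.3.2 abstracts procedures from the hospital record. Section 10.4.7.1 has the DSMB review the main listed safety endpoints. Section 10.3 gives no collection window, so cover may be incomplete, but the route does not depend on the SAE label. In addition, 8.3 has a general sentence requiring all on-study AEs to be documented, and 8.4.1 sets an entry deadline for non-serious AEs during hospitalization. These blur the 24-hour limit but do not replace it: 8.3 itself states the limit by start date.
- *Seriousness under 8.2.1 controls all safety reporting.* Unanticipated problems are reportable whether or not they are SAEs (8.4.3). Unanticipated device effects have their own definition (8.1.3) and deadline (8.4.2). Neither uses CTCAE grade.
- *A typical 72-hour ECPR run extends well past the 24-hour window, so most complications are affected.* That is a share of time. The documents give no timing of events.
- *Every 4.2.2 event defined by a procedure is an SAE.* Section 8.1.2 asks whether the intervention prevented permanent impairment or damage. The documents do not say that every such procedure meets that test.

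**Conclusion.** Wrong as written. The protocol has two rules for an SAE, the 8.2.1 rule is the narrower, and no order of precedence is given. The disagreement lies wholly in grades 1 to 3, and in every disagreeing case the event is serious under 8.1.2 and 8.4 and non-serious under 8.2.1.

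The consequence is limited but real. For onset after 24 hours, the choice of rule decides whether the event is inside the AE recording window, in the DSMB's SAE listing and in the final SAE summary. Because predefined safety endpoints have their own capture route, the effect is mainly on the SAE record itself and on events outside the composites.

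Its size in events cannot be estimated from the documents. The proportion of patients with any SAE may move little, since 8.1 expects most patients to have at least one; the event-level listing is more exposed. No stopping boundary depends on the count.

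The conclusion assumes that the note is applied as a definition, and that the explicit 24-hour limit in 8.2.1, 8.3 and 8.4.1 governs over the general sentence in 8.3. The CTCAE term criteria are in the manual of procedures, not in these documents, so the grade of any particular complication could not be checked.

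**What to change.** Reconcile 8.2.1 with 8.1.2 and 8.4 in one of two ways: delete the grade-based SAE sentence, or keep it and add that it does not limit the 8.1.2 definition. In either case, state that seriousness is determined by the 8.1.2/8.4 definition alone and that CTCAE grade is recorded as a separate item.

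The cost is one sentence deleted or qualified, brief retraining at one site, and probably a few more SAE forms. No endpoint, sample size or analysis method changes.
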